
research centre
 
Sun yat-sen university memorial hospital The Third Affiliated Hospital of Sun Yat-sen University Southern hospital of southern medical university Zhujiang hospital of southern medical university The Third Affiliated Hospital of Southern Medical University

Efficacy evaluation
 
Imaging evaluation by independent review experts according to the specific situation of patients, determine the evaluation time and evaluation method.

Data management and statistical analysis
 
SAS 9.4 statistical software was used for statistical analysis. Unless otherwise specified, all statistical tests will use a one-sided test with $\alpha=0.05$ and the confidence intervals will use a one-sided 95% confidence interval.

Estimated Start and End Time: Start Time: June 2022; End: April 2026

II. introduction

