5.4 Statistical analysis

5.4.1 Sample size and calculation basis

The historical control pCR rate was assumed to be 10% based on recent clinical studies. The expected pCR estimate for this study was 25%, representing a clinically significant improvement. The resulting zero and alternative assumptions are as follows:

The original assumptions to be tested were: h_0 : PCR rate = 25%

Corresponding alternative hypothesis: h_a : pcr rate > 25%

The Simon Phase II (Simon, 1989) design will be used to test the superiority of the combination

of neoadjuvant therapy with Ampley monoclonal antibody as compared with the historical control. The expected Class I error rate for the project (ineffective study drug but effective promotion) $\alpha=0.05$, with 80% confidence. An interim efficacy and safety analysis will be performed when 18 subjects are enrolled. Of the 18 subjects in the first phase, the second phase was not performed if < 2 effective cases of complete pathological response were achieved. If there were ≥ 2 valid cases in Phase 1, continue with Phase 2 until there are a total of 43 subjects. If the total effective cases in the first and second stages were not less than 7, it could be determined that the pCR of the new adjuvant therapy in this study was significantly improved compared with the historical control, thereby demonstrating the superiority and efficacy of the new adjuvant therapy in this study. A 10% dropout rate was considered for this study, which required the recruitment of a total of 48 subjects. The statistical design was calculated using an online statistical tool approved by the Design Department of Sun Yat-sen Memorial Hospital, Sun Yat-sen University (<http://cancer.unc.edu/biostatistics/program/ivanova/simonstwostageDesign.aspx>) (Ivanova & Deal, 2016).

5.4.2 data analysis set

Safety analysis set: Includes all patients who received at least 1 dose of any study drug (any component of neoadjuvant combination therapy).

Efficacy analysis set: Includes all patients who received at least 1 dose of any study drug treatment (any component of neoadjuvant combination therapy) followed by radical cystectomy.

5.6.3 Statistical analysis plan.

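### The null hypothesis is printed as pCR = 25%, which is the target rate; the design and its success rule test against the 10% historical rate

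*Protocol*

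**What the plan says.** Everything on this point is in protocol section 5.4.1, Sample size and calculation basis.

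- Historical rate: "The historical control pCR rate was assumed to be 10% based on recent clinical studies".
- Target rate: "The expected pCR estimate for this study was 25%, representing a clinically significant improvement".
- Null hypothesis, presented as following from those two rates: "The original assumptions to be tested were: h_0 : PCR rate = 25" per cent.
- Alternative: "Corresponding alternative hypothesis: h_a : pcr rate > 25" per cent.
- Error rates: a type I error of 0.05 (the programme summary makes all tests one-sided unless otherwise specified), "with 80% confidence".
- First stage: "Of the 18 subjects in the first phase, the second phase was not performed if < 2 effective cases of complete pathological response were achieved".
- Final rule: with at least 2 responses in stage 1, continue to 43 patients. At least 7 responses in total is taken to show a significant improvement over the historical control.
- Recruitment: 48, allowing for 10% dropout.

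Section 5.4.3.1 defines the primary endpoint but restates no hypothesis. Section 5.2.6 repeats only the stage 1 stopping count. Section 5.4.1 is therefore the sole formal statement of the primary test.

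**The concern.** In a Simon design the null is the uninteresting rate, here the historical 10%, and the target rate is the point at which power is set. Section 5.4.1 gives both rates correctly and then prints the target in both hypothesis lines.

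Three things fail as a result. The null no longer corresponds to the historical control that the same section says the design is meant to beat. The success count corresponds to an observed rate below the null it is supposed to reject. The 80% figure has no alternative to refer to, because the expected rate now equals the null.

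At stake is the meaning of the primary result. An analyst who tests the printed hypothesis needs far more responses than the count rule asks for. A report that follows the count rule and says the null was rejected would, on the printed wording, be claiming a pCR above 25% without support.

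**Working it through.** **Inputs** (section 5.4.1, with one-sidedness from the programme summary): p0 = 0.10, p1 = 0.25, one-sided α = 0.05, power 0.80, n1 = 18, N = 43, continue if at least 2 of 18, succeed if at least 7 of 43, dropout 10%. The 80% is read as power, which is the only role it can have in this design.

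**Formula.** For a rule that continues if X1 ≥ a and succeeds if the total is ≥ r:

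P(success | p) = Σ from x = a to 18 of P(X1 = x) × P(Y ≥ r − x), with X1 ~ Bin(18, p) and Y ~ Bin(25, p).

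**1. Reproduce the plan's sample size.** An exact search over two-stage designs up to N = 50, with p0 = 0.10 and p1 = 0.25, gives this design as the one with the smallest expected size under p0:

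- n1 = 18, stop at ≤ 2 responses; N = 43, succeed at ≥ 8.
- Type I error at 10%: 0.0480. Power at 25%: 0.8003.
- Probability of early stopping at 10%: 0.7338. Expected size: 18 + (1 − 0.7338) × 25 = 24.7.
- Recruitment: 43 / 0.90 = 47.8, rounded up to 48.

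The stage size, total and recruitment figure all match the protocol. The sample size rests on a 10% null and a 25% alternative.

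**2. Compare the success count with the printed null.** 7 / 43 = 16.3%. Under a rate of 25% the expected count is 0.25 × 43 = 10.75. The threshold lies below the value it would have to exceed.

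**3. Apply the printed rule when the printed null is true (p = 0.25).**

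| Rule | P(success) at pCR = 25% |
|---|---|
| As printed: ≥ 2/18, then ≥ 7/43 | 0.9153 |
| Simon optimal boundaries: ≥ 3/18, then ≥ 8/43 | 0.8003 |

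Under the printed null these would be type I errors, against a stated 0.05. Under a 10% null they are power at the design alternative, and the second row is the intended 80%.

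**4. What a real test of 25% would need.** For a single-stage X ~ Bin(43, 0.25):

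- P(X ≥ 16) = 0.0514, above 0.05.
- P(X ≥ 17) = 0.0252.

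So the requirement is 17 / 43 = 39.5%. If pCR were exactly the expected 25%, this test would succeed only 2.5% of the time.

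**5. Where the two readings disagree.** Totals of 7 to 16 succeed under the count rule and fail a 5% test of 25%. Ignoring the interim stop, the probability of such a total at a true pCR of 25% is P(X ≥ 7) − P(X ≥ 17) = 0.9388 − 0.0252 = 0.914.

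**The case against.** The strongest reply is that the intention is plain. The design is described as testing superiority over the historical control, success is described as improvement over that control, and the decision is fixed in counts. A reader who follows those sentences recovers the 10% null and does not conclude that pCR exceeds 25%. The text also reads as translated, so the wrong value may have arisen there.

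Much of this stands. The design is sound in its stage sizes and total, and the harm arises only if the hypothesis lines are taken as printed. But 25% appears in both the null and the alternative, nothing elsewhere corrects it, and the protocol does not leave the hypothesis open for a later document. Whatever its cause, the formal primary hypothesis is wrong.

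Two narrower cautions are fair. First, reproducing 18 and 43 does not prove that 10% and 25% are the only rates that could lead there. Other pairs, for example 5% against 20% with different cut-offs, admit some 18/43 rule with 5% error and 80% power. The argument needs only that the protocol's own two rates reproduce the design and that a 25% null is incompatible with success at 7 of 43. Second, correcting the null does not rescue the printed cut-offs. At a true pCR of 10% they give a type I error of 0.122. That is a separate defect in the same section.

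**Conclusion.** The concern holds. The printed null and alternative contradict the stated historical rate, the design they are said to lead to, and the success rule. Taken literally, the rule rejects the printed null 91.5% of the time when it is exactly true, and every total from 7 to 16 of 43 is a success or a failure depending on which sentence is followed.

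The figures assume independent binomial responses and exactly 18 and 43 evaluable patients; the 17-response requirement is for a single-stage test. The sample size is unaffected. The correction must be made, because this is the only statement of the hypothesis on which the primary conclusion will rest.

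**What to change.** In section 5.4.1:

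- Write H0: pCR ≤ 10% and Ha: pCR > 10%, with the sample size set at a design alternative of 25%.
- Replace the 80% confidence wording with 80% power at a pCR of 25%.
- State that meeting the success rule supports a pCR above 10%, and does not show that it exceeds 25%.

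For this point the cost is a wording amendment: stage sizes, total and recruitment stay at 18, 43 and 48.

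Reconcile the cut-offs in the same amendment, here and where the stage 1 count is repeated in section 5.2.6. Otherwise a correct hypothesis would sit beside a rule with a 12.2% error at 10%. The boundaries that match the stated error and power are to continue at ≥ 3 of 18 and succeed at ≥ 8 of 43 (error 0.0480, power 0.8003).

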Clinical Study Protocol

Protocol Name: A Clinical Study of Disitamab Vedotin for Injection Combined With Penpulimab Injection in Neoadjuvant Therapy for Patients With HER2-expressing Cisplatin-intolerant cT2-T4aNxM0 Bladder Urothelial Carcinoma

Sponsor: Sun Yat-sen Memorial Hospital, Sun Yat-sen University

Version number: V1.0

Version date: 2022.5.1

Signature confirmation of scheme:

Compliance Statement

In compliance with the Provisions of the Good Laboratory Practice Regulations, Administrative Measures for Investigator-initiated Clinical Studies in Medical and Health Institutions (for Trial Implementation) and the Declaration of Helsinki, participants pledged to conduct this study in accordance with this protocol. Participants must be trained to conduct the study after obtaining the written approval of the Ethics Committee and the informed consent of the subjects. Protocol modifications need to be re-approved.

I. programme summary

Project Name: A Clinical Study of Disitamab Vedotin for Injection Combined With Penpulimab Injection in Neoadjuvant Therapy for Patients With HER2-expressing Cisplatin-intolerant cT2-T4aNxM0 Bladder Urothelial Carcinoma

Abbreviation of Scheme: RC48-C039

Test purpose:
 
To evaluate the efficacy and safety of neoadjuvant treatment with Disitamab Vedotin for Injection Combined With Penpulimab Injection in patients with cT2-T4aNxM0 bladder urothelial carcinoma and HER2-expressing cisplatin intolerance.

Test brief:
 
The single-armed, exploratory clinical study of vidicon monoclonal antibody combined with pie Ampley monoclonal antibody designed for cisplatin-intolerant patients with cT2-T4aNxM0 bladder urothelial carcinoma in this study confirmed the effectiveness and safety of the new adjuvant treatment of vidicon monoclonal antibody combined with pie Ampley monoclonal antibody for cisplatin-intolerant patients with cT2-T4aNxM0 bladder urothelial carcinoma, and finally provided new evidence-based evidence for new adjuvant treatment of such patients.

Sample size:
 
This is a prospective clinical study. It is intended to collect 48 patients with cT2-T4aNxM0 bladder urothelial cancer who are HER2-expressing and cisplatin-intolerant, and all of them have received neoadjuvant treatment with vidicon monoclonal antibody in combination with pie Ampley monoclonal antibody.

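### The Simon cut-offs (at least 2 of 18, at least 7 in total) give a type I error of 0.122 at the planned 43 patients, not 0.05, and no denominator is fixed if more than 43 are evaluable

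*Protocol*

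**What the plan says.** Section 5.4.1 gives the design inputs: "The historical control pCR rate was assumed to be 10% based on recent clinical studies", and "The expected pCR estimate for this study was 25"%. It names a Simon two-stage design with a type I error rate of 0.05 and 80% as the second operating characteristic, which can only be power. The programme summary makes all tests one-sided at 0.05 unless otherwise specified.

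The decision rule has three parts:

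- Stage one has 18 subjects, and stage two is not run if fewer than 2 reach pCR. Section 5.2.6 repeats this as a ground for terminating the study.
- Otherwise the trial is to "continue with Phase 2 until there are a total of 43 subjects".
- The verdict then turns on one final count of pCRs: "If the total effective cases in the first and second stages were not less than 7", the regimen is judged significantly better than the historical control.

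A 10% dropout allowance follows, "which required the recruitment of a total of 48 subjects". The programme summary repeats the figure: "It is intended to collect 48 patients with cT2-T4aNxM0 bladder urothelial cancer".

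The efficacy set (part III, item 2.2, and section 5.4.2) is every patient who received at least one dose and then had a radical cystectomy. Neither place caps it at 43.

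**The concern.** A Simon rule is a pair of absolute counts calibrated to exact stage sizes. If a count is off by one, or is applied to a different number of patients, the error rates are no longer those stated. Here the counts look one too low for the planned 43. In addition, the number evaluable could lie on either side of 43.

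The verdict of the trial is at stake. Seven pCRs would be reported as superiority to the historical control, whether that is 7 of 43 (16.3%) or 7 of 48 (14.6%).

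The denominator is also partly discretionary. Under section 5.2.4, the team leader unit decides whether patients operated on outside the time limits are eligible for analysis, and no criterion is given. In an open-label trial with an absolute cut-off, one such decision could settle the result.

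**Working it through.** **Inputs.** From section 5.4.1: p0 = 0.10, p1 = 0.25, alpha = 0.05 (one-sided, programme summary), power 80%, n1 = 18, N = 43, dropout 10%. The same section prints the null hypothesis as a pCR rate of 25%. That contradicts its own 10% control and is a separate inconsistency. The figures below use 10% as the null.

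**Formula.** With c1 the count needed to continue, c the count needed for success and n the number evaluable:

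P(success | p) = sum over x from c1 to 18 of P(X1 = x) × P(X2 ≥ c − x), where X1 ~ Bin(18, p) and X2 ~ Bin(n − 18, p).

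**Step 1: the plan's sample sizes.** A full search at 10% versus 25%, alpha 0.05 and power 80% gives an optimal design with n1 = 18 and N = 43. The drug is rejected at ≤ 2 of 18 or ≤ 7 of 43, with alpha 0.0480 and power 0.8003. Inflation gives 43/0.9 = 47.8, rounded up to 48. The sizes 18, 43 and 48 therefore reproduce.

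**Step 2: the plan's cut-offs at n = 43, p = 0.10.** In the optimal design, 2 and 7 are the largest counts at which the drug is rejected. The protocol uses 2 as the smallest count to continue and 7 as the smallest count for success. For the written rule (c1 = 2, c = 7):

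| x in stage 1 | P(X1 = x) | P(X2 ≥ 7 − x), 25 patients | product |
|---|---|---|---|
| 2 | 0.2835 | 0.0980 | 0.0278 |
| 3 | 0.1680 | 0.2364 | 0.0397 |
| 4 | 0.0700 | 0.4629 | 0.0324 |
| 5 | 0.0218 | 0.7288 | 0.0159 |
| 6 | 0.0052 | 0.9282 | 0.0049 |
| ≥ 7 | 0.0012 | 1 | 0.0012 |

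The sum is 0.122 (0.1218 before rounding the terms). Power at 25% is 0.915. Correcting only the final count (≥ 2, ≥ 8) gives 0.0575. Correcting only the interim count (≥ 3, ≥ 7) gives 0.0940. Both must change to reach 0.0480.

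**Step 3: the same rules at other evaluable numbers.**

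| n evaluable | written rule (≥ 2, ≥ 7): alpha | Simon (≥ 3, ≥ 8): alpha / power | ≥ 3, ≥ 9: alpha / power |
|---|---|---|---|
| 43 | 0.122 | 0.048 / 0.800 | 0.021 / 0.730 |
| 44 | 0.132 | 0.053 / 0.810 | 0.024 / 0.748 |
| 45 | 0.142 | 0.057 / 0.819 | 0.027 / 0.764 |
| 46 | 0.153 | 0.062 / 0.826 | 0.030 / 0.777 |
| 47 | 0.163 | 0.067 / 0.832 | 0.033 / 0.790 |
| 48 | 0.174 | 0.072 / 0.838 | 0.036 / 0.800 |

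**Step 4: how likely is more than 43?** Assume each of 48 recruits is evaluable independently with probability 0.9. This is an assumption that matches the planned dropout. Then P(more than 43) = 0.47 and P(all 48) = 0.9^48 = 0.006. Averaged over the evaluable number, alpha is 0.124 for the written rule and 0.049 for the Simon cut-offs.

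**The case against.** The strongest reply concerns the 48. Inflating 43 to 48 for dropout is ordinary practice. Read in order, section 5.4.1 attaches the count of 7 to two stages totalling 43 and mentions 48 only afterwards. How to handle surplus evaluable patients is often left to a statistical analysis plan, and one may exist that is not shown. Under the planned dropout the mismatch barely matters on average: about 0.001 for the Simon cut-offs (0.048 to 0.049) and 0.003 for the written ones (0.122 to 0.124).

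Most of this stands. A reader might infer that recruiting 48 is what drives the false-positive rate to 17%. The document does not support that reading. The rate is already 0.122 at the planned 43. Moving to 48 adds 5.2 points to the written rule, and only with no dropout at all. On correct cut-offs it adds at most 2.4 points. A reader might also infer a shortfall in power if fewer than 43 are evaluable. Under the written rule power is still 0.858 at 38; the 0.724 at 38 belongs to the corrected cut-offs.

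The reply does not touch the cut-offs. The protocol itself fixes them, together with the alpha that they miss, and a later plan cannot be presumed to overrule them.

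**Conclusion.** The decision rule as written does not deliver its stated error rate. At the planned 43 patients the one-sided type I error against 10% is 0.122, nearly two and a half times 0.05, because both cut-offs are one below the Simon design whose sample sizes the protocol uses. This is the main defect and must be corrected.

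The missing link between count and denominator is secondary. It takes the written rule to 0.132–0.174, and the correct one to 0.053–0.072, if 44 to 48 patients are evaluable and the count is applied unchanged. That application is one possible reading of an uncapped efficacy set, not something the protocol states. The link still deserves a sentence, because with correct cut-offs a single patient beyond 43 already takes alpha above 0.05.

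The figures rest on exact binomial calculation, a 10% null and a stage one of exactly 18 evaluable patients. The averages also assume that being evaluable is independent of outcome.

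**What to change.** 1. In section 5.4.1, and in the matching termination ground in section 5.2.6, change the rule to: stop at 2 or fewer pCRs among 18, and require at least 8 among 43.
2. Add to section 5.4.1 that the decision uses the first 43 evaluable patients in enrolment order, with the 18 of stage one counted on the same basis, and that any further evaluable patients are reported descriptively. This holds alpha at 0.048 and power at 0.800.
3. If all evaluable patients are to enter the decision instead, prespecify a cut-off for each possible number. Requiring at least 9 at 44 to 48 (after at least 3 of 18) holds alpha at 0.024–0.036. Power is then only 0.748–0.790 at 44 to 47 and reaches 0.800 only at 48, and the protocol should state that cost. Option 2 is the better choice.

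The change is to wording and needs no extra patients. The price is a stricter test. Power at 25% goes from 0.915 to the protocol's own target of 0.800. The chance of stopping after stage one rises from 0.450 to 0.734 if the true rate is 10%, and from 0.039 to 0.135 if it is 25%.

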5.2.6 Study termination

Study termination was defined as the point in time when the final data from the clinical study was collected, that is, the point in time when the last study patient completed his/her last visit to the study center, and was expected to occur 2 years and 4 months after the last patient was enrolled in the study. The team leader unit has the right to terminate the study at any time. Reasons for early termination of the study may include, but are not limited to, 1) the incidence or severity of AEs in

this or other studies are suggestive of a health hazard to the patient; 2) The overall patient enrollment is unsatisfactory; 3) In the first stage (18 subjects), the effective cases with complete pathological response were less than 2.

If a decision is made to terminate the study, each investigator will be notified by the team leader unit. Patients who discontinue early should be viewed as soon as possible and scheduled for a drug safety/end-of-treatment visit, if necessary. The investigator may be notified to follow additional procedures to ensure that adequate consideration is given to the protection of the patient's interests. The investigator will be responsible for informing the Institutional Review Board (IRB)/Independent Ethics Committee of the premature termination of the study.

5.3 Study evaluation and procedures.

Patient safety and tolerability will be closely monitored throughout the study. All evaluations of each patient should be performed and documented in the medical records. Dosing will only occur after review of clinical assessments and local laboratory values, which must be obtained before each dose, and when dosing conditions are met as directed by the study protocol.

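### Both two-stage pCR cut-offs are one too low (go at ≥2/18, success at ≥7/43), so the one-sided type I error is about 12%, not the stated 5%

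*Protocol*

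**What the plan says.** Section 5.4.1 gives the design inputs: "The historical control pCR rate was assumed to be 10% based on recent clinical studies", and "The expected pCR estimate for this study was 25%, representing a clinically significant improvement". It names a Simon (1989) two-stage design and states the error rates as "ineffective study drug but effective promotion) $\alpha=0.05$, with 80% confidence". The programme summary makes all tests one-sided at 0.05.

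The decision rules in the same section are:

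- **Stage 1, 18 patients:** "the second phase was not performed if < 2 effective cases of complete pathological response were achieved". With 2 or more, recruitment continues to 43.
- **Final, 43 patients:** "If the total effective cases in the first and second stages were not less than 7, it could be determined" that pCR is significantly better than the historical control, which the section treats as proof of superiority and efficacy.

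Section 5.2.6 repeats the stage 1 rule as a reason for ending the study: "In the first stage (18 subjects), the effective cases with complete pathological response were less than 2". The total of 43 is raised to 48 for 10% dropout.

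**The concern.** In a Simon design the published boundaries r1 and r are rejection counts: stop if stage 1 responses are r1 or fewer, and conclude the regimen is not promising if total responses are r or fewer. For these inputs the optimal design has r1 = 2 and r = 7. The protocol has the same two numbers beside the same two sample sizes, but as the lowest counts that count in the regimen's favour. Each cut-off is therefore one response too lenient.

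The final count is the trial's only stated success criterion, and section 2.1 says the results should guide a phase III trial. If the count is too low, a regimen no better than the historical rate is called superior more often than the protocol says. If the stage 1 count is too low, such a regimen more often goes on to full enrolment.

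**Working it through.** **Inputs** (section 5.4.1; one-sidedness from the programme summary): p0 = 0.10, p1 = 0.25, alpha = 0.05 one-sided, power 0.80, n1 = 18, n = 43, so n2 = 25. Written rule: continue if X1 ≥ 2, succeed if the total is ≥ 7.

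**Step 1. Reproduce the plan's sample size.** An exhaustive search of two-stage designs up to n = 50, with type I error ≤ 0.05 and power ≥ 0.80, gives as the design with the smallest expected size under p0: n1 = 18, r1 = 2, n = 43, r = 7. Its type I error is 0.0480 and its power 0.8003. The dropout step also agrees: 43/0.9 = 47.8, rounded up to 48. So 18, 43 and 48 reproduce, and the design behind them has boundaries 2 and 7 as rejection counts.

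**Step 2. Probability of declaring success.** For a rule that continues at X1 ≥ a1 and succeeds at a total ≥ a:

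P(success | p) = Σ over x ≥ a1 of P(X1 = x) × P(X2 ≥ a − x), with X1 ~ Bin(18, p) and X2 ~ Bin(25, p).

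At p = 0.10:

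| x in stage 1 | P(X1 = x) | P(X2 ≥ 7 − x) | Product, success at ≥7 | P(X2 ≥ 8 − x) | Product, success at ≥8 |
|---|---|---|---|---|---|
| 2 | 0.2835 | 0.0980 | 0.0278 | 0.0334 | 0.0095 |
| 3 | 0.1680 | 0.2364 | 0.0397 | 0.0980 | 0.0165 |
| 4 | 0.0700 | 0.4629 | 0.0324 | 0.2364 | 0.0165 |
| 5 | 0.0218 | 0.7288 | 0.0159 | 0.4629 | 0.0101 |
| 6 or more | | | 0.0060 | | 0.0049 |

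- Written rule (≥2, ≥7): 0.0278 + 0.0397 + 0.0324 + 0.0159 + 0.0060 = **0.1218**.
- Simon rule (≥3, ≥8): 0.0165 + 0.0165 + 0.0101 + 0.0049 = **0.0480**.

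**Step 3. Early stopping and expected size at p = 0.10.**

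- Written rule: P(X1 ≤ 1) = 0.1501 + 0.3002 = 0.4503; expected n = 18 + 25 × 0.5497 = 31.7.
- Simon rule: P(X1 ≤ 2) = 0.4503 + 0.2835 = 0.7338; expected n = 18 + 25 × 0.2662 = 24.7.

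**Step 4. All four combinations.** Power is from the same sum at p = 0.25.

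| Continue at | Succeed at | Type I error (10%) | Power (25%) | Early stop (10%) | Expected n (10%) |
|---|---|---|---|---|---|
| ≥2/18 (written) | ≥7/43 (written) | 0.1218 | 0.915 | 45.0% | 31.7 |
| ≥2/18 | ≥8/43 | 0.0575 | 0.860 | 45.0% | 31.7 |
| ≥3/18 | ≥7/43 | 0.0940 | 0.840 | 73.4% | 24.7 |
| ≥3/18 (Simon) | ≥8/43 (Simon) | 0.0480 | 0.800 | 73.4% | 24.7 |

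**Step 5. Other readings of the success count.** Ignoring the interim look, ≥7 of 43 has type I error 0.133. If the count of 7 were applied to all 48 recruited, keeping the ≥2/18 look, it would be 0.174. Neither comes near 0.05.

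**The case against.** **The hypotheses are printed differently.** Section 5.4.1 writes the null hypothesis as "The original assumptions to be tested were: h_0 : PCR rate = 25" per cent, not 10%. The 12% figure depends on taking 10% as the null. That reading is sound: the section defines success as improvement over the historical control, sets that control at 10%, and 10% versus 25% reproduces 18 and 43. The printed null is a separate error and does not rescue the rule: at a true rate of 25% the written rule succeeds with probability 0.915.

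**The cause is inferred.** The section does not say that the optimal variant was chosen, prints no r1 or r, and the software output is not shown. That rejection counts were turned into go counts is a strong inference from four matching numbers, no more. The finding does not need it, because the written counts fail the stated alpha whatever their origin. Likewise, 80% is called confidence in the text and is read here as power.

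**The two cut-offs do not contribute equally.** This stands. Correcting the final count alone brings type I error from 0.122 to 0.058; correcting the first alone brings it only to 0.094. The lax stage 1 rule is mainly a loss of efficiency, and the protocol promises no particular early-stopping probability. Even so, 0.058 still exceeds 0.05, so the first cut-off cannot be left alone.

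**Translation slip.** The English is visibly a translation, and the success count appears only once. But the stage 1 rule appears consistently in two sections, and nothing in the document corrects either cut-off.

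**Conclusion.** The point holds. With a null pCR rate of 10%, the written rules give a one-sided type I error of 0.122 against the stated 0.05, about 2.4 times as large. A regimen at the historical rate passes the interim look 55% of the time instead of 27%, and about 7 more patients are treated on average (31.7 − 24.7). Power at 25% is 0.915, above the stated 80%, so the error is entirely in the direction of false success.

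This rests on three assumptions: 10% is the null, 80% is power, and the final count is taken at exactly 43 evaluable patients. The corrected type I error of 0.048 also needs the stage 1 stop to be followed. If it were ignored, ≥8 of 43 alone would have type I error 0.061.

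Because the error sits in the primary decision rule, it must be corrected before the result is judged.

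**What to change.** - **Section 5.4.1:** stop after stage 1 if 2 or fewer of 18 patients have a pCR; continue to 43 if 3 or more do; declare superiority over the historical control only if 8 or more of 43 have a pCR.
- **Section 5.2.6:** give the stage 1 reason for termination as 2 or fewer of 18, and word it as a binding rule in line with 5.4.1. At present it stands in a list of reasons that may lead to termination.
- **Section 5.4.1, same amendment:** state the null as a pCR rate of 10% and call the 80% power, so that the hypotheses match the rule.

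The cost is a wording amendment. The sample sizes 18, 43 and 48 do not change. The success bar rises by one response, and power at 25% falls from 0.915 to 0.800, which is what the protocol already claims. The counts hold only at 43: applied to 48 evaluable patients, ≥3/18 with ≥8 would have type I error 0.072. The amendment should therefore tie the final count to 43.
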